9.4. PK Parameters Derivation: Attainment of Steady State for FIX Activity

Attainment of steady state will be estimated using aggregate assessment of trough concentration if sufficient data will be available.

To assess whether steady state was achieved for FIX activity after daily dosing of CB2679d, aggregate assessment of trough concentration will be used to evaluate attainment of steady state (Maganti et al 2008). The approach is based on the comparison of log-transformed normalized trough concentration values for each dose to the mean of the results for all the following doses.

This analysis will be done using repeated measures analysis only if the data are sufficient to support; i.e., analysis will be carried out only on subjects who have at least 3 valid FIX activity level results out of 6 pre-dose samples). Alternatively, analysis of variance (ANOVA) comparison will be carried out on log-transformed Cmin (concentration at the end of the dosing interval = FIX activity level pre-dosing) pre-dose on days 2, 3, 7, 14, 21 and 28. The following SAS code may be used to conduct the analysis:

PROC MIXED;

CLASS <time> <subject>;

MODEL log_base_e_ <FIX actual level> = <time> /DDFM = KR;

LSMEANS <time>;

RUN;

The DDFM = KR (Kenward Roger) option performs the degrees-of-freedom calculations detailed by Kenward and Roger (1997).

Contrasts will be tested between a time point and the pooled mean over all remaining time points. For example, the following contrasts will be tested as example:

- Day 3 vs Days 7, 14, 21, and 28
- Day 7 vs Days 14, 21, and 28
- Etc.

The first non-significant comparison will be concluded to be the dosing interval at which steady state concentration are attained. The p-value for difference of Least Square Means (LSM), Geometric Mean Ratio, and the 95% confidence interval (CI) for the contrasts will be provided.

This document is confidential.

Statistical Analysis Plan for Interventional Studies
Sponsor: Catalyst Biosciences, Inc.; Protocol No.: DLZ-201

10. Analysis of Pharmacodynamics

PD analysis will be performed using SAS statistical package version 9.4 or higher. PD analysis will be performed for PD and Safety Population.

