	14.2.2.4.2	FIX Activity Level: Summary of Subjects who Achieve a FIX Activity Level > 50% (PK Population)
	14.2.2.4.3	FIX Activity Level: Summary of Subjects who Achieve a FIX Activity Level > 30% (Safety Population)
	14.2.2.4.4	FIX Activity Level: Summary of Subjects who Achieve a FIX Activity Level > 50% (Safety Population)
14.2.3		Analysis: Attainment of Steady State
	14.2.3.1	Analysis of Attainment of Steady State for CB2679d by Repeated Measures ANOVA (PK Population)
	14.2.3.2	Analysis of Attainment of Steady State for CB2679d by Repeated Measures ANOVA (Safety Population)
14.3		Safety Data Summary Tables
14.3.1		Adverse Events
	14.3.1.1	Treatment Emergent Adverse Events (TEAE) - Overall Summary (Safety Population)
	14.3.1.2	Treatment Emergent Adverse Events by System Organ Class and Preferred Term (Safety Population)
	14.3.1.3	Treatment Emergent Adverse Events by Relationship to Study Drug by System Organ Class and Preferred Term (Safety Population)
	14.3.1.4	Treatment Emergent Adverse Events by System Organ Class, Preferred Term and Maximum Severity (Safety Population)
	14.3.1.5	Treatment Emergent Serious Adverse Events by System Organ Class and Preferred Term (Safety Population)

This document is confidential.

Statistical Analysis Plan for Interventional Studies
Sponsor: Catalyst Biosciences, Inc.; Protocol No.: DLZ-201

Header	Table Number	Name (Analysis Population)
	14.3.1.6	Treatment Emergent Serious Adverse Events by Relationship to Study Drug by System Organ Class and Preferred Term (Safety Population)
	14.3.1.7	Treatment Emergent Adverse Events Leading to Study Drug Discontinuation by System Organ Class and Preferred Term (Safety Population)
	14.3.1.8	Adverse Events of Special Interest by System Organ Class and Preferred Term (Safety Population)
14.3.2		Listings of Deaths, Other Serious and Significant Adverse Events
14.3.4		Laboratory Evaluation and Vital Signs
14.3.4.1		Clinical Laboratory Data
14.3.4.1.1		Hematology Data
	14.3.4.1.1.1	Clinical Laboratory Tests: Hematology - Summary of Actual and Change from Baseline (Safety Population)
	14.3.4.1.1.2	Clinical Laboratory Tests: Hematology - Shift from Baseline in Laboratory Value (Safety Population)
14.3.4.1.2		Chemistry Data
	14.3.4.1.2.1	Clinical Laboratory Tests: Chemistry - Summary of Actual and Change from Baseline (Safety Population)
	14.3.4.1.2.2	Clinical Laboratory Tests: Chemistry - Shift from Baseline in Laboratory Value (Safety Population)
14.3.4.2		Vital Signs

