6.2.1 Baseline and Change from Baseline	Maximum absolute change from baseline will be calculated as the maximum of the absolute changes from baseline over all visits during treatment period.	Maximum change from baseline will be calculated as the maximum of the changes from baseline over all visits during treatment period.
8.2.1 Change in FIX levels from pre-dose	Actual and change from baseline (including maximum absolute change from baseline) values for FIX activity level will be summarized by time point for the PK and the Safety Population. Different PK parameters will be summarized as well as described in Section Error! Reference source not found.	Actual and change from baseline (including maximum change from baseline) values for FIX activity level will be summarized by time point for the PK and the Safety Population. Different PK parameters will be summarized as well as described in Section Error! Reference source not found.
9.3.2 Listing and Presentation of Individual PK Data	The following figures will be produced: Individual intense PK concentration-time provided for FIX activity levels with all subjects in the same figure on linear scales.	The following figure will be produced: Box plots of PK concentration provided for FIX activity levels by visits.
9.3.3 Summary of PK Concentrations and Parameter in Plasma		Added: Geometric CV = sqrt (exp ((log (geometric SD)) ^2) - 1) * 100%
9.4 PK Parameters Derivation: Attainment of Steady State for FIX Activity		Added: REPEATED <time> /type = un SUBJECT = <subject>
10.2 PD Biomarkers Analysis	Actual and change from baseline (including maximum absolute change from baseline) for all PD parameters (e.g., Prothrombin Time, aPTT, Fibrinogen, D-dimer, F1+2, and TAT) will be summarized by time point. Coagulation assays and thrombogenicity markers will be tabulated separately.	Actual and change from baseline (including maximum change from baseline) for all PD parameters (e.g., Prothrombin Time, aPTT, Fibrinogen, D-dimer, F1+2, and TAT) will be summarized by time point. Coagulation assays and thrombogenicity markers will be tabulated separately. Added: In case that thrombogenicity markers are below limit of quantification, then all analysis are done with the imputed midpoint of the potential values

This document is confidential.

Note to File, 24-July-2020
Sponsor: Catalyst Biosciences; Protocol No.: DLZ-201

Section	Revised from	Revised to

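### SAP 9.4 leaves open when the steady-state test switches to an ANOVA, and the repeated-measures covariance it now specifies cannot be fitted with 6 subjects and 6 troughs

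*SAP*

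**What the plan says.** SAP 9.4 compares each log trough with the mean of the later ones, using pre-dose samples on Days 2, 3, 7, 14, 21 and 28. On the model it says: "This analysis will be done using repeated measures analysis only if the data are sufficient to support", and explains that "analysis will be carried out only on subjects who have at least 3 valid FIX activity level results out of 6 pre-dose samples". It then continues: "Alternatively, analysis of variance (ANOVA) comparison will be carried out on log-transformed Cmin".

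One optional PROC MIXED block follows both sentences. It contains "CLASS <time> <subject>" and "MODEL log_base_e_ <FIX actual level> = <time> /DDFM = KR", with no RANDOM or REPEATED statement, so in SAP V1.0 subject plays no part in the fit. The July 2020 Note to File adds to Section 9.4 the line "REPEATED <time> /type = un SUBJECT = <subject>". Its visible rows leave the ANOVA sentence as it was.

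The decision rule is: "The first non-significant comparison will be concluded to be the dosing interval at which steady state concentration are attained". SAP 17 indexes two outputs for this analysis, Table 14.2.3.1 (PK Population) and Table 14.2.3.2 (Safety Population). Both titles name a repeated measures ANOVA, and neither table is marked as the one that decides.

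**The concern.** Two models are permitted and nothing fixes when one gives way to the other. The 3-of-6 condition is a filter on subjects. The model that now has within-subject structure asks for more covariance parameters than the planned sample can supply, and no simpler structure is named as a fallback. An analyst whose fit fails has one other written option, the ANOVA, and the SAP does not say that it must contain a subject term.

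The choice matters because the rule rewards imprecision. An ANOVA on day alone puts between-subject variation into the error of a within-subject contrast. That widens the standard error, makes early contrasts non-significant and so brings forward the declared day. What is at stake is the SAP's only formal test of steady state.

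**Working it through.** The plan gives no SD, correlation, standard error or power for this analysis, so there is no figure of its own to reproduce.

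**Inputs from the documents.** 6 subjects (SAP 3.5); 6 troughs (SAP 9.4); half-life 63.2 h, and levels of 20% rising to above 30% after IV plus SC dosing (Protocol V2.0, 2.2.2). **Assumptions.** Two-sided 5%, taken from the 95% CI; normal subject intercepts and residuals on the log scale; SDs as stated below.

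**1. Can the unstructured covariance be fitted?** Six time points need 6 × 7 / 2 = 21 parameters. With a separate mean for each day, 6 complete subjects leave a residual covariance of rank 6 − 1 = 5, below the 6 required. It is singular, and the REML fit is not estimable as written. Seven complete subjects would only just reach rank 6. Dropping Day 2 (15 parameters, rank 5 of 5) would also sit exactly at the limit.

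**2. Standard error of a day-only ANOVA.** For a contrast with weights c summing to zero, the correct SE is sw × sqrt(Σc²/6). The day-only model uses sqrt(sb² + sw²) × sqrt(Σc²/6). The ratio is 1/sqrt(1 − rho), with rho = sb²/(sb² + sw²).

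| rho | 0 | 0.2 | 0.5 | 0.8 | 0.9 |
|---|---|---|---|---|---|
| SE ratio | 1.00 | 1.12 | 1.41 | 2.24 | 3.16 |

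**3. One contrast by hand.** Take sb = 0.3 and sw = 0.15, so rho = 0.09/0.1125 = 0.8. For Day 7 against Days 14, 21 and 28, Σc² = 1 + 3/9 = 1.333 and sqrt(1.333/6) = 0.471.

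- Subject-adjusted: SE 0.15 × 0.471 = 0.071; significant beyond 2.060 × 0.071 = 0.146 (25 df).
- Day only: SE 0.335 × 0.471 = 0.158; significant beyond 2.042 × 0.158 = 0.323 (30 df).
- Without a load, the trough as a fraction of plateau is 1 − 2^(−24(d−1)/63.2): 0.794, 0.967, 0.995 and 0.999 on Days 7, 14, 21 and 28. The expected log difference is −0.231 − (−0.013) = −0.218. The adjusted model detects that gap; the day-only model usually does not.
- With a load, taking 30 − 10 × 2^(−24(d−2)/63.2), the Day 7 difference is 3.308 − 3.396 = −0.088, inside both limits. The Day 3 difference is 3.105 − 3.374 = −0.268. With Σc² = 1.25, the limits are 0.141 and 0.313, so it falls between them.

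**4. Simulation.** 20,000 trials per setting, 6 subjects by 6 troughs, first p ≥ 0.05 taken as steady state, day-only (30 df) against subject-adjusted (25 df).

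| Trough profile | SD between / within | First contrast | Trials naming different days |
|---|---|---|---|
| Rising, no load | 0.3 / 0.15 | Day 7 | 66% (Day 7 declared: 81% day-only, 16% adjusted) |
| Rising, no load | 0.2 / 0.2 | Day 7 | about 30% |
| Rising, no load | 0.4 / 0.1 | Day 7 | about 91% |
| Loaded, 20% to 30% | 0.3 / 0.15 | Day 7 | 15% to 22%, depending on how the rise is drawn |
| Loaded, 20% to 30% | 0.3 / 0.15 | Day 3 | 66% |
| With or without load | 0.08 / 0.15 | Day 3 or 7 | 6% to 12% |
| Flat from Day 2 | 0.08 to 0.4 / 0.06 to 0.2 | Day 2, 3 or 7 | 5% or less |

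In the rising settings with between-subject variation, the day-only model names the earlier day in about 95% or more of disagreements. At rho 0 the models differ in only 2% to 4% of trials.

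**5. What the documents say about spread.** The prior study's IQR of 14.9% to 16.6% gives a total log SD of ln(16.6/14.9)/1.349 = 0.108/1.349 = 0.08. One of those five subjects was not above 12%, so the tail is wider than the IQR suggests. None of this separates between-subject from within-subject variation, so rho stays unknown.

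**The case against.** A reader might infer that the plan specifies an ANOVA with no subject term. The text does not go that far. There is one code block, the Note to File adds a subject structure to it without limiting that line to one model, both table titles say repeated measures, and no day-only ANOVA table is indexed. The day-only fit is something the wording allows, not a planned output. What stands is that the added structure cannot be fitted at the planned size and the alternative is left undefined.

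A reader might also say there is no rule at all for choosing a model. There is a condition, and it turns on missing samples, not on results. It still does not say when the analysis as a whole switches.

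The strongest tempting reading is that the primary endpoint depends on this choice. It does not. SAP 8.1 and Tables 14.2.1.1 and 14.2.1.2 count subjects above 12% during treatment and make no use of the 9.4 result.

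Section 9.4 also refers to normalized troughs. Normalizing within subject would remove most of the between-subject variation, but no normalizer is defined, and both the ANOVA sentence and the code use the measured pre-dose level.

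The two-population point is minor. A subject who stops before the Day 7 sample has at most the Day 2 and Day 3 troughs and fails the 3-of-6 filter in either table. The populations will differ mainly through deviation exclusions or a stop at about Day 7.

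**Conclusion.** The concern holds in a limited form. The unstructured covariance is not estimable from 6 subjects at 6 time points; that follows from the design and needs no assumption about variances. The switch to the ANOVA is undefined, and a day-only version would overstate the contrast standard errors by 1/sqrt(1 − rho) and lean towards an early steady-state day.

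The size of that lean is not established. The SE ratio is 1.4 at rho 0.5 and 2.2 at rho 0.8, but the documents give no rho. Disagreement ranges from about 6% to over 90% across the assumed rising profiles and non-zero between-subject SDs, and is 5% or less with flat troughs. The figures of 81% against 16% apply to an unloaded profile with assumed SDs; they should not be read as a forecast for this trial, in which every subject receives an IV load. The consequence is confined to Tables 14.2.3.1 and 14.2.3.2.

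**What to change.** In SAP 9.4, delete the ANOVA alternative and replace the Note to File's REPEATED line with type=un by one prespecified model for all eligible subjects: log trough, day as fixed effect, `RANDOM INTERCEPT / SUBJECT=<subject>`, Kenward-Roger degrees of freedom. State explicitly that this replaces the unstructured line and does not sit alongside it. The model has two variance parameters and can be estimated with 6 subjects.

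As a secondary change, label Table 14.2.3.1 (PK Population) as the result and Table 14.2.3.2 (Safety Population) as supportive.

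The cost is one sentence, one line of code and one table label. There are two downsides: steady state may be concluded at a later day than under a day-only ANOVA, and a random intercept assumes equal correlation between all pairs of troughs, however far apart.

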Interim results showed PK and activity of CB2679d as 22-fold greater potency over BeneFIX® and longer mean residence time. Single-dose bioavailability was 18.2-23.6%, SC beta $t_{1/2}$ was 66-103 hours and time that CB2679d is present at the maximum concentration in serum (T_{max}) was 6-24 hours. One subject reported transient fever and a mild SC injection site reaction. Cohort 4 was omitted as sufficient data had been gained from single dosing SC in Cohorts 2 and 3. The SC dose in Cohort 5 was reduced from 300 IU/kg to 150 IU/kg daily. PK and activity

Dalcinonacog alfa_DLZ-201 VERSION 2.0, Amendment 1

levels after 6 daily doses in 5 subjects reached a median of 15.7% [interquartile range 14.9% to 16.6%] Four of 5 subjects had levels above 12%. Half-life was 63.2 hours [interquartile range 60.2 to 64.0 hours]. The interim study results support the aim of achieving normal or high mild hemophilia FIX levels in individuals with hemophilia B with repeated SC dosing. Mild pain, erythema and redness was reported at the injection site in initial injections and not a later injection. One subject reported these adverse events to be moderate for the first 2 injections and mild thereafter. An IV loading dose has been added to cohort 6 in this study to see if it eliminates injection site adverse events as they are believed to be due to low FIX levels because of washout of prior treatment ([Figure 2](#)).

The nadir activity after IV plus SC dosing was 20% in both subjects in cohort 6 and thereafter levels increased to >30%. It is clear that the IV loading dose increased the bioavailability of SC CB2679d by increasing the saturation of the extravascular compartment and resulted in greater activity levels than simple addition of SC to IV activity. Neutralizing antibodies developed in both subjects (transiently in one subject). A root cause analysis determined that the most likely cause was a 3-month gap between dosing in cohort 5 and cohort 6 in these 2 participants ([Figure 3](#)).

FIGURE 2. CB2679D PHASE 1/2 OPEN LABEL STUDY DESIGN

[figure not shown]

IV, intravenous; SC, subcutaneous.

^aFirst SC dose 30 minutes post-IV.

Dalcinonacog alfa_DLZ-201 VERSION 2.0, Amendment 1

FIGURE 3. CB2679D PHASE 1/2 STUDY: COHORT 5 & 6 FIX ACTIVITY RESULTS

Dalcinonacog alfa_DLZ-201 VERSION 2.0, Amendment 1

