9.2. Plasma PK Endpoints

Various pharmacokinetic parameters will be calculated as listed below, including:

- clearance (CL) (from Day 28 and subsequent samples during washout)
- volume of distribution at steady state (Vz) (from Day 28 and subsequent samples during washout),
- Highest recorded clotting activity level after nadir value from the IV infusion
- and terminal (beta phase) half-life $t_{1/2}$, will be calculated from Day 28 and subsequent samples during washout

A semiparametric model described by Lee et al. (Lee et al, 1990) will be used to calculate the terminal $t_{1/2}$. This analysis will be performed using the program Demitasse 2000 (Lee et al, 1997). Other parameters will be calculated using a standard non-compartmental approach.

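### SAP 9.4 can report a time to SC steady state that lies before the IV nadir, because troughs dominated by the Day 1 IV load enter the contrasts

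*SAP*

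**What the plan says.** SAP 9.4 describes its method as a "comparison of log-transformed normalized trough concentration values for each dose to the mean of the results for all the following doses". The trough points are given as "FIX activity level pre-dosing) pre-dose on days 2, 3, 7, 14, 21 and 28". A subject enters the analysis with "at least 3 valid FIX activity level results out of 6 pre-dose samples", and the count of six is reached only if Days 2 and 3 are both included. The decision rule is: "The first non-significant comparison will be concluded to be the dosing interval at which steady state concentration are attained". The contrasts written out, which are labelled as examples, begin with "Day 3 vs Days 7, 14, 21, and 28". The later Note to File adds a repeated-measures statement with unstructured covariance to 9.4 and leaves the time points and the decision rule alone.

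Each subject receives 50 IU/kg IV and then 100 IU/kg SC daily from the same day (SAP 3.7). On the earlier study, Protocol 2.2.2 (Version 2.0, Amendment 1) says: "The nadir activity after IV plus SC dosing was 20% in both subjects in cohort 6 and thereafter levels increased to >30" (percent). SAP 9.2 allows for this shape in a different endpoint, the "Highest recorded clotting activity level after nadir value from the IV infusion". SAP 9.4 contains no such condition.

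**The concern.** Comparing each trough with the mean of all later ones works when troughs climb from below to a plateau. An early trough then lies clearly under the later mean, and the first non-significant contrast marks the approach to the plateau. An IV load breaks that pattern. The early troughs start high and fall while the SC contribution is still building. On the way down, a trough can equal the average of a low nadir and a high plateau without anything being at steady state. The rule tests only for a difference and stops at the first contrast that shows none.

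The output at risk is the reported time to SC steady state, Tables 14.2.3.1 and 14.2.3.2. A Day 2 or Day 3 answer would describe the decaying load rather than the SC regimen. The entry rule adds to the problem: a subject with valid samples on Days 2, 3 and 7 only is admitted without contributing a single plateau trough.

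**Working it through.** The plan gives no error rate or power for this test, so there is no figure of its own to reproduce.

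**Inputs from the documents.** Half-life 63.2 h after repeated SC dosing; upper end of the single-dose SC range 103 h; SC bioavailability 18.2–23.6%; 20 h IV fall-off used for baseline adjustment in the earlier study (all Protocol 2.2.2); doses and 6 subjects (SAP 3.3, 3.7). **Assumed.** Trough profiles, day of the nadir, IV recovery, within-subject log SD 0.1–0.3, and a two-sided 5% test (suggested by the 95% CI in 9.4).

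**1. SC build-up.** After n daily doses the trough is 1 − 2^(−24n/T) of plateau.

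| Trough | n | T = 63.2 h | T = 103 h |
|---|---|---|---|
| Day 2 | 1 | 23% | 15% |
| Day 3 | 2 | 41% | 28% |
| Day 7 | 6 | 79% | 62% |
| Day 14 | 13 | 97% | 88% |

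The terminal-phase residual of the load at Day 14 is the complement, 2^(−312/T): 3% at 63.2 h and 12% at 103 h.

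**2. IV share of the trough.** Assume the same disposition for both routes. On Day 2 the load supplies 50/(50 + 100F), which is 50/73.6 = 68% to 50/68.2 = 73%. On Day 3, with r = 2^(−24/T), the share is 50r²/(50r² + 100F(r + r²)). Over T from 20 to 103 h this is 39–56%; by Day 7 the same calculation gives 2–23%. If SC is instead calibrated to the earlier SC-only cohort (median 15.7% after 6 doses of 150 IU/kg) with IV recovery of 0.5–1.3 IU/dL per IU/kg, the shares are 78–93% on Day 2 and 47–84% on Day 3.

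**3. The coincidence by hand.** Take assumed troughs of 28, 20, 25, 31, 32, 32% on Days 2 to 28, which fit the reported nadir and rise. The geometric mean of the last five is exp[(ln 20 + ln 25 + ln 31 + 2 ln 32)/5] = 27.55. The Day 2 ratio is 28/27.55 = 1.02, although Day 3 is 20% and the plateau is 32%.

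**4. Simulating the rule.** Six subjects, subject-level contrasts on the log scale (t, 5 df), stopping at the first p > 0.05. Only the Day 2 value changes; the later five stay as in step 3. Within-subject log SD is 0.2.

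| Day 2 trough | Ratio to later mean | Day 2 declared steady state |
|---|---|---|
| 24% | 24/27.55 = 0.87 | 76% |
| 28% | 1.02 | 94–95% |
| 30% | 30/27.55 = 1.09 | 88% |
| 32% | 32/27.55 = 1.16 | 73% |
| 35% | 35/27.55 = 1.27 | 42% |
| 40% | 40/27.55 = 1.45 | 9% |

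Across log SD 0.1–0.2, the 24% and 32% cases range over 23–77%. With 60 subjects the 28% case still stops at Day 2 in about 79–90% of trials, while the 24% and 32% cases fall to essentially 0%. If troughs rise steadily from Day 2, the share is about 0%.

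**5. Later nadir, or a Day 3 start.** With the nadir on Day 7 (30, 25, 20, 31, 32, 32%), Day 2 is declared in 66–92% of trials over log SD 0.1–0.3. If testing starts at Day 3, Day 3 is declared in 42–89%, still before the nadir. In the SC-only-calibrated model with a 20 h IV half-life, recovery 0.5 gives Day 2 in 19–84%. Recovery 1.0 gives Day 2 in 0–3% but Day 3 in 12–79%, with the calculated nadir on Day 5.

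**6. Moving the start.** With the step 3 profile and a Day 7 start, Day 7 (still rising) is declared in 2%, 48% and 73% at log SD 0.1, 0.2 and 0.3. With a Day 14 start, where 31% is compared with 32%, Day 14 is declared in 92–95%.

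**The case against.** - **The primary endpoint.** A reader might infer that the primary result is biased, because the endpoint is worded in terms of steady state. The documents do not support that. SAP 8.1 and Tables 14.2.1.1 and 14.2.1.2 count subjects with FIX above 12% during the treatment period and never call on 9.4. In the step 3 profile even the nadir is above 12%. What remains is that 9.4 is the SAP's only assessment of steady state.
- **The start day.** The contrasts written out begin at Day 3. If that is the intended start, Day 2 cannot be declared, and with a nadir on Day 3 itself the Day 3 contrast stops the search in only 0–9% of trials at log SD 0.1–0.2. This stands as an ambiguity. The list is marked as examples, the trough list and the six-sample count include Day 2, and a Day 3 start still fails if the nadir comes later.
- **Power.** It is tempting to call this pure bias that no sample size could cure. That is true only near exact coincidence; in the 24% and 32% cases 60 subjects remove it.
- **Thin evidence for the shape.** The reported nadir comes from two subjects, both of whom developed neutralizing antibodies (one transiently). Its day is not in the text and the figures are not shown. If the nadir falls at or before the Day 2 trough, the mechanism disappears.
- **Visibility.** Levels are summarised by time point, listed individually and box-plotted by visit, and "Geometric Mean Ratio, and the 95% confidence interval (CI) for the contrasts will be provided". A careful reader could spot a false Day 2 answer, but the stated conclusion would still be wrong.
- **Day 7.** It would be too strong to say that Days 2, 3 and 7 carry no steady-state information. At 62–79% of plateau, Day 7 carries some.

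**Conclusion.** The point holds in limited form. Followed as written, SAP 9.4 can name a time to SC steady state that precedes the IV nadir: Day 2, or Day 3 if testing starts there and the nadir is later. The effect falls on Tables 14.2.3.1 and 14.2.3.2, not directly on the primary count.

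Its frequency cannot be settled from the documents, because IV recovery, the day of the nadir and the within-subject variability are not given. Under the assumed profiles it runs from about 0% to 95% of 6-subject trials. It is highest when the Day 2 trough happens to lie near the geometric mean of the later ones; away from that point much of it reflects low power. Load dominance is well supported for Day 2 (at least 68% of the trough) and depends on the assumptions for Day 3 (39–84%). Since SAP 9.2 already allows for the nadir, leaving it out of 9.4 is a gap that should be closed.

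**What to change.** In SAP 9.4:

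1. Remove Days 2 and 3 from the contrasts, report them descriptively, and allow a steady-state conclusion only from troughs after the IV nadir.
2. As the simplest pre-specified form, begin at Day 14: Day 14 against Days 21 and 28, then Day 21 against Day 28. Show Day 7 against the later days with its ratio and 95% CI as supportive only.
3. Replace the entry rule of 3 out of 6 samples with at least 2 of the Day 14, 21 and 28 pre-dose samples.
4. Make the geometric mean ratio and its 95% CI the main result, with the significance rule secondary.

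The cost is a changed contrast list and some wording; no new data are needed. Steady state could no longer be claimed before Day 14. The change also does not make non-significance in 6 subjects good evidence: at a 103 h half-life, where Day 14 is only 88% of plateau, the shortened rule still declares Day 14 in 61–86% of simulated trials. Item 4 is there for that reason.
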